12.1 Sample size and analysis

The primary hypothesis is that ^{99m}Tc -rhAnnexin V-128 SPECT carotid imaging can detect apoptosis. We anticipate that the prevalence of positive ^{99m}Tc -rhAnnexin V-128 SPECT carotid scans will be about 0.3 to 0.5 of the patients. A sample size of 30 patients produces a 95% confidence interval with a precision of about 0.17 to 0.20 when the estimated proportion is 0.3 to 0.5. Sample size was also estimated for the comparison of ^{99m}Tc -rh-Annexin-V 128 uptake in asymptomatic patients with carotid disease versus normals using a 5% significance level and power of 95%. The measured neck uptake in 12 normals was $0.8 \pm 0.27\%$ ID/gm in the Phase I study. Assuming a similar SD of 0.27% ID/gm in the patients and a minimal clinically important difference (MCID) of 50% or a change of 0.4 in uptake, the required sample size is 9 normals and 25 patients. Allowing for attrition, we plan to recruit 10 normals and 35 patients.

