4.2.1.1 Inclusion criteria

For all participants:

- 1. Males and females age 18 years or greater;
- 2. Able and willing to comply with the study procedures;
- 3. Negative pregnancy test for women of childbearing potential at screening and on the day of administration of ^{99m}Tc-rhAnnexin V-128.

For participants with carotid artery disease:

4. Evidence of 50% or more carotid stenosis in one or more carotid arteries on carotid ultrasound within 10 years;

For control participants:

4. No significant carotid artery disease on carotid ultrasound.

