4.3.3.5 Ultrasound Examination

Clinical evidence of 50% or more carotid stenosis in one or more carotid arteries on carotid ultrasound within 10 years prior to enrolment is required for inclusion in the trial.

Evidence of 50% or more carotid stenosis has to be confirmed in a more recent US imaging within 8 weeks prior to ^{99m}Tc-rhAnnexin V-128 administration. If not confirmed, the participant will be declared as a screening failure.

B-mode and color Doppler ultrasound studies will be acquired of both carotid arteries and performed with an ultrasound scanner equipped with a 5- to 7-MHz transducer. Plaque morphology, as echogenicity, defined as reflectance of the emitted ultrasound signal, will be assessed as previously described and graded from 1 to 4 as echolucent, predominantly echolucent, predominantly echogenic, or echogenic. The vessel lumen will be used as the reference structure for defining echolucency, and the bright echo zone produced by the media-adventitia interface in the far wall will be used as the reference structure for defining echogenicity. Interobserver reproducibility of plaque morphology in stenotic arteries has been previously assessed (κ =0.56, 95% C.I. 0.38 to 0.74).

The degree of stenosis will be calculated by the following equation: (1-PSVr/PSVs)×100%, where PSVr denotes peak systolic velocity at the point of reference (here, the distal carotid artery) and PSVs the peak systolic velocity in the stenosis.

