6.1.2.3 Secondary endpoints

The secondary endpoints of Phase II and the related statistical analysis are:

- Descriptive statistics of ^{99m}Tc-rhAnnexin V-128 uptake in patients vs control participants will be presented by areas of interest (left carotid, right carotid, thoracic aorta, abdominal aorta and aortic arch) and by time points to assess the background uptake profile and the pathologic profile. Comparison of uptake in patients vs controls at each timepoint will be explored by the most appropriate test i.e. two sample t-test.
- The relationship between carotid uptake (separately for left and right) and ultrasound grade of plaque echolucency/echogenicity (1 echolucent, 2 predominantly echolucent, 3 predominantly echogenic, 4 echogenic) will be assessed for all patients using box plots and

Version: 01 Page: **26 of 167**

summaries of uptakes by the levels of echolucency/echogenicity for each time point. Only carotids with stenosis (defined as \geq 50% as per protocol) will be included in this analysis (i.e. a patient with only 1 carotid with stenosis \geq 50% will contribute data for that carotid uptake value and the associated plaque echolucency/echogenicity value for the same carotid, patients with stenosis in both carotids will contribute data on uptake and echolucency/echogenicity for each of their carotids).

Association between carotid and aortic uptake will be assessed for patients and controls, by time
point, using scatter plots. All carotids with ≥ 50% stenosis (as described above) will be included
in this plot, and different colours/symbols will be used for left and right carotid results. If further
investigation is considered appropriate, the correlation coefficients (Pearson's or Spearman's)
within left carotids and right carotids separately will be calculated.

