6.1.20 Significance testing and estimation

All statistical tests will be two-sided at the 5% level of significance.

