		95% C.I.	99.9 - 99.9	99.9 - 99.9
	Negative	n (%)	99 (99.9)	99 (99.9)
	Missing	n (%)	99 (99.9)	99 (99.9)

Source: Data listings {Specify data listing number(s)} Analysis dataset: {Specify datasets}

Notes: All percentages are based upon the number of enrolled subjects by group.

Confidence intervals are estimated using the exact (Clopper-Pearson) formula for binomial proportions.

^{*} Patient = Subject with asymptomatic plaque; Control = Healthy volunteer

[#] Subjects with either a positive scan at 60 or 120 minutes post injection will be considered overall positive

Version: 01 Page: **93 of 167**

Table 14.2.1.3: Patient Carotid and Aorta Imaging Assessment – Comparison between time points – FAS Population

60 MINS AFTER IP INJECTION	120 MINS AFTER IP INJECTION	STATISTIC	PATIENT* (N=xx)
Positive	Positive	n (%)	99 (99.9)
Positive	Negative	n (%)	99 (99.9)
Positive	Total	n (%)	99 (99.9)
Negative	Positive	n (%)	99 (99.9)
Negative	Negative	n (%)	99 (99.9)
Negative	Total	n (%)	99 (99.9)
Total	Positive	n (%)	99 (99.9)
Total	Negative	n (%)	99 (99.9)
Total	Total	n (%)	99 (99.9)
		p-value	0.9999

Source: Data listings {Specify data listing number(s)} Analysis dataset: {Specify datasets}

Notes: All percentages are based upon the number of subjects who performed both imaging procedures.

p-value is based on McNemar's test.

^{*} Patient = Subject with asymptomatic plaque

Version: 01 Page: **94 of 167**

Table 14.2.1.4: Left Carotid Uptake Imaging Assessment – Target to Background Ratio (TBR) – FAS Population

TIME POINT	STATISTIC	PATIENT* (N=xx)	CONTROL* (N=xx)
60 mins after IP injection	n	99	99
	Missing	99	99
	Mean	99.9	99.9
	S.D.	99.9	99.9
	Median	99.9	99.9
	Q1, Q3	99.9, 99.9	99.9, 99.9
	Min, Max	99, 99	99, 99
	p-value^		0.9999
120 mins after IP injection	n	99	99
•	Missing	99	99
	Mean	99.9	99.9
	S.D.	99.9	99.9
	Median	99.9	99.9
	Q1, Q3	99.9, 99.9	99.9, 99.9
	Min, Max	99, 99	99, 99
	p-value^		0.9999

Source: Data listings {Specify data listing number(s)} Analysis dataset: {Specify datasets}

^p-value is based on T- test.

^{*} Patient = Subject with asymptomatic plaque; Control = Healthy volunteer

Version: 01 Page: **95 of 167**

Table 14.2.1.5: Right Carotid Uptake Imaging Assessment – Target to Background Ratio (TBR) – FAS Population

TIME POINT	STATISTIC	PATIENT* (N=xx)	CONTROL* (N=xx)
60 mins after IP injection	n	99	99
	Missing	99	99
	Mean	99.9	99.9
	S.D.	99.9	99.9
	Median	99.9	99.9
	Q1, Q3	99.9, 99.9	99.9, 99.9
	Min, Max	99, 99	99, 99
	p-value^		0.9999

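### No analysis compares the stenosed carotid with the same patient's other carotid, so higher uptake in patients than in volunteers need not localise to plaque

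*SAP*

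**What the plan says.** Patients qualify with "Evidence of 50% or more carotid stenosis in one or more carotid arteries" (SAP 4.2.1.1; the same criterion is in Protocol 8.1). SAP 4.3.3.5 states that "B-mode and color Doppler ultrasound studies will be acquired of both carotid arteries". Listing 16.2.4.2 holds stenosis for each side, and Listing 16.2.6.2 holds the target-to-background ratio (TBR) for each carotid at each time point.

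SAP 6.1.2.3 uses these data in three ways:

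- Patients v controls by region and time point, with a two-sample t-test. Tables 14.2.1.4 and 14.2.1.5 show left and right carotid TBR with the note that the "p-value is based on T- test". Neither table is restricted by stenosis, so a one-sided patient's other artery enters as an ordinary patient value.
- Uptake by plaque grade, in carotids at 50% or more only, with box plots and summaries. Here "a patient with only 1 carotid with stenosis" at that level contributes that side alone.
- Scatter plots of carotid against aortic uptake, again limited to carotids at 50% or more, with correlation coefficients if judged useful.

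The McNemar test in Table 14.2.1.3 compares time points, not sides. Protocol 12.2 names a paired t-test among possible methods without attaching it to any contrast. SAP 6.1.17 allows an optional look at level of stenosis as a covariate, with no method and no table.

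**The concern.** The primary hypothesis is that the scan detects apoptosis in carotid plaque (Protocol 5.1, SAP 4.1.1.1). The planned tests of carotid uptake compare patients referred to cardiology clinics or diagnostic imaging with healthy volunteers whose laboratory values are normal (Protocol 8.3, SAP 4.3.1). The controls are to be age and sex matched (SAP 4.2.1), but other differences between the groups remain. If patients show higher uptake, the plan cannot separate uptake at the stenosis from uptake that is generally higher in such patients.

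A one-sided patient carries a reference artery in the same scan, after the same injection. The difference between the two arteries cancels whatever is common to that patient. The data for it are already collected and listed, but the plan never forms the difference.

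**Working it through.** **1. The protocol's own sample size.** Inputs from Protocol 12.1: "using a 5% significance level and power of 95"%, "Assuming a similar SD of 0.27% ID/gm in the patients", and a minimal difference of "50% or a change of 0.4 in uptake" (half of 0.8). SAP 6.1.20 fixes the sidedness: "All statistical tests will be two-sided at the 5% level of significance". With an allocation of 25 patients to 9 controls:

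controls = (1 + 9/25) × [0.27 × (1.960 + 1.645) / 0.4]² = 1.36 × 5.92 = 8.05, rounded up to 9, with 25 patients.

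The stated 9 and 25 reproduce. Exact t-test power is 95.9% at 9 v 25 and 98.1% at the recruited 10 v 35.

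**2. Precision of the planned comparison.** SE = 0.27 × √(1/10 + 1/35) = 0.0968, or 0.359 SD. With 43 degrees of freedom (t = 2.017), the 95% CI half-width is 0.195 %ID/gm.

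**3. Precision of a within-patient contrast.** Let n be the number of patients with exactly one carotid at 50% or more, and ρ the left-right correlation of uptake. Then SE = 0.27 × √(2(1 − ρ)/n), and the half-width is SE × t on n − 1 degrees of freedom. Neither n nor ρ is in the documents, so both are assumed over a range. The SD is taken as equal in both arteries and both groups.

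| One-sided patients n | Half-width, ρ = 0 | ρ = 0.5 | ρ = 0.7 | ρ that gives 0.195 |
|---|---|---|---|---|
| 10 | 0.273 | 0.193 | 0.150 | 0.49 |
| 15 | 0.211 | 0.150 | 0.116 | 0.15 |
| 20 | 0.179 | 0.126 | 0.098 | below 0 |
| 25 | 0.158 | 0.111 | 0.086 | below 0 |
| 30 | 0.143 | 0.101 | 0.078 | below 0 |

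The last column is ρ = 1 − n × (0.195 / t)² / (2 × 0.27²). Other values are 0.83 at n = 5, 0.63 at n = 8, 0.35 at n = 12 and −0.06 at n = 18. From about 18 one-sided patients, then, the paired interval is narrower for any ρ of 0 or more.

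**4. Where it goes the other way.** At n = 10 and ρ = 0.3 the paired SE is √(2 × 0.7/10) = 0.374 SD, larger than 0.359. At n = 15 and ρ = 0 it is √(2/15) = 0.365 SD, also larger.

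**5. Scale.** The SD of 0.27 is in %ID/gm, while the SAP tables analyse TBR, for which no SD is given. The half-widths therefore hold only on the %ID/gm scale. The break-even values of n and ρ do not depend on the SD.

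**The case against.** The strongest reply is that no stated aim is left unanswered. The objectives cover prevalence of abnormal scans, uptake in controls, uptake by plaque echogenicity, and carotid-aortic correlation; none asks for stenosed v non-stenosed artery. Protocol 12.4 calls the primary analysis mainly descriptive and the inferential work exploratory. This stands, and it limits the point to an improvement. It does not remove it, because the hypothesis concerns plaque and a same-patient contrast bears on that more directly than a comparison with volunteers.

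A reader might infer that the trial leans on a less precise comparison, or that the planned test is underpowered. The documents do not support either reading. Precision depends on two quantities they do not give, and for plausible values it can favour the planned test. Power for the protocol's own difference is 98%. Nor can the power of the two contrasts be compared at one common effect size, because they estimate different things: the contralateral artery may hold plaque below 50%, which would probably shrink the within-patient difference.

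Three further replies have weight. TBR is already scaled to the participant's own background, so some shared noise is gone and ρ may be low; that affects precision, but TBR does not remove a general difference in arterial uptake between patients and volunteers. The definition of an abnormal scan still needs the control database (SAP 6.1.2.2). And nothing is lost from the listings, so the contrast could be run later; but then it would be chosen after the results are known.

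**Conclusion.** The gap is real and the remedy is nearly free: a cheap improvement. The plan specifies no within-patient contrast between the stenosed and the contralateral carotid, although each side's stenosis and uptake are recorded. As planned, higher uptake in patients would not by itself show that the uptake lies at the plaque.

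The main gain is validity. Added precision is conditional: the paired 95% CI is narrower than that of 35 v 10 with about 18 or more one-sided patients at any ρ of 0 or more, or with fewer at moderate correlation (above about 0.15 at 15 patients, 0.49 at 10). This assumes a common SD. With few one-sided patients and low correlation, the paired interval is wider.

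**What to change.** Add one exploratory table to SAP 6.1.2.3, worded for example:

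*In patients with exactly one carotid at 50% stenosis or more, the within-patient difference in uptake (stenosed minus contralateral) will be summarised at each time point with mean, 95% CI and a paired t-test (Wilcoxon signed-rank as a check).*

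Report the number of one-sided patients beside it. State that the contralateral artery may carry plaque below 50%, so the difference is a separate estimand that probably understates the contrast with a plaque-free artery. Keep the patient-control comparison and the control-based cut-off for an abnormal scan unchanged.

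The cost is one table and one result per time point, with no new procedure or data. The t-test procedure named in SAP 12.2 can run the paired test; the signed-rank check would need a procedure added to that list. The extra p-values fall under the existing rule of no multiplicity adjustment (SAP 6.1.19) and should be labelled exploratory.

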6.1.3 Safety endpoint(s)

Safety and tolerability will be primarily evaluated by the incidence of adverse events, clinical laboratory values (hematology, blood chemistry and urinalysis), development of anti-Annexin V-128 antibodies, vital signs (blood pressure and heart rate) and physical examination findings.

All safety data will be included in the data listings and summary tables will be based on the safety population. The statistical analysis of safety data will be mainly descriptive in nature.

6.1.3.1 Adverse events

All original AE/SAE terms will be coded using the Medical Dictionary for Regulatory Activities (MedDRA) Version 19.0.

Adverse events (AEs) will be listed on an individual basis, including relationship and severity, LLT (Lowest Level Term) and verbatim term. Treatment emergent Adverse events (TEAEs) and Adverse Drug Reactions (ADRs) will be summarized by System Organ Class (SOC) and Preferred Term (PT), grouping patients versus control subjects, and also including a total column for all subjects who received Annexin. Participants with more than one adverse event within a particular SOC and PT will be counted only once for that SOC and PT reporting the highest level in severity. The incidence of TEAEs and ADRs will also be summarized by subject type and severity.

Listings and summaries of serious adverse events (SAEs), adverse events leading to withdrawal and listings of deaths will also be presented.

Treatment Emergent Adverse Events and Adverse Drug Reactions will be defined as below:

Version: 01 Page: **27 of 167**

- Treatment Emergent Adverse Events: Events that emerge after the ^{99m}Tc-rhAnnexin V-128 injection and up to 30 days after the injection that were absent before it or worsen relative to the pre-treatment state.
- Adverse Drug Reactions: Treatment emergent adverse events possibly or probably related to study treatment.

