10.2 Laboratory Assessments

Blood samples for hematology, biochemistry and urinalysis will be obtained at baseline for screening, 30 +/- 3 days post IP administration and following any adverse events.

In case of clinically significant abnormalities in baseline laboratory values, the participant will be declared as a screening failure.

Study Protocol

Hematology	Coagulation	Blood Chemistry	Urinalysis

 • WBC with differential • RBC • Platelets • Hb • MCV • Hematocrit 	
 • PT • PTT • INR 	
 • BUN • Uric acid • Albumin • Direct bilirubin • LDH • Calcium • Chloride • Phosphorus • Total cholesterol • Total protein • Serum creatinine • Total bilirubin • AP • AST/ASAT • ALT/ALAT • Gamma-GT • Sodium • Potassium • Glucose • β-HCG at screening 	
 • Dipstick test¹ • Pregnancy test (before injection of study product, if applicable)

¹ In case one of the assessments of the dipstick test is positive, a microscopic analysis of the urine must be performed.

Laboratory Assessments will be performed by the [REDACTED] [REDACTED] The Ottawa Hospital according to Ministry of Health and Long Term Care (MHLTC) standards.

10.3 ^{99m}Tc-rhAnnexin V-128 Planar and SPECT Imaging of the Carotid Arteries and Aorta and Image Analysis

Planar and SPECT imaging of the carotids and aorta will be performed 60 and 120 minutes after injection of tracer.

Administration of the ^{99m}Tc-rhAnnexin V-128 (350 MBq \pm 10 %) will be as a single bolus via an intravenous catheter in an antecubital vein followed by a saline flush. Negative pregnancy test for women of childbearing potential will be confirmed on the day of administration.

All images will be acquired with a dual head SPECT/CT gamma camera with low-energy high-resolution collimators. The energy acceptance window for the ^{99m}Tc photopeak will be 140 keV (+/- 10%). A low dose CT scan (helical, 120 kVp, 1 mA with 1.9 pitch) will be acquired of the neck, thorax and abdomen for attenuation correction.

Study Protocol

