13.1 Definition of Adverse Events

An AE is defined as any untoward medical occurrence in a participant and which does not necessarily have a causal relationship with the investigational product. An AE can therefore be any unfavourable and unintended sign (including an abnormal laboratory finding), symptom, or disease, temporally associated with the use of an investigational product, whether or not causally related to the investigational product.

AEs will be reported, if applicable, from the signing of the informed consent until the last study-related procedure.

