6.1.3.2 Clinical laboratory values

Hematology, blood chemistry, urinalysis and immunogenicity values are recorded at baseline for screening, 30 ± 3 days post IP administration and following any adverse events. Descriptive statistics including shift tables will be generated for all laboratory tests performed i.e. the actual values and the changes from pre-injection.

Data listing will be ordered by subject and measuring time. Listings of abnormal results (both clinically and non-clinically relevant) will also be reported.

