6.1.12 Visit windows

The screening visit can occur anytime within 8 weeks before the injection day (Day 0).

The first follow-up visit (phone call) should occur within 24 hours after the injection. The second follow-up visit should occur 30 days after the injection with a window of 3 days, i.e. the visit has to be performed between the 27th and the 33rd day from the ^{99m}Tc-rhAnnexin V-128 administration.

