Treatment emergent SAEs	n (%) [n. events]	99 (99.9) [99]	99 (99.9) [99]	99 (99.9) [99]
Treatment emergent serious adverse drug reactions	n (%) [n. events]	99 (99.9) [99]	99 (99.9) [99]	99 (99.9) [99]
Treatment emergent AEs leading to withdrawal	n (%) [n. events]	99 (99.9) [99]	99 (99.9) [99]	99 (99.9) [99]
Treatment emergent AEs leading to death	n (%) [n. events]	99 (99.9) [99]	99 (99.9) [99]	99 (99.9) [99]

Source: Data listings {Specify data listing number(s)} Analysis dataset: {Specify datasets}

Note: Format is number of subjects (percent of subjects) [number of events].

^{*} Patient = Subject with asymptomatic plaque; Control = Healthy volunteer

Version: 01 Page: **102 of 167**

Table 14.3.1.2: Number (%) of Subjects Reporting Treatment Emergent Adverse Events by Primary System Organ Class and Preferred Term – Safety Population

PRIMARY SYSTEM ORGAN CLASS PREFERRED TERM	STATISTIC	PATIENT* (N=xx)	CONTROL* (N=xx)	ALL SUBJECTS (N=xx)
Any adverse events	n (%)	99 (99.9)	99 (99.9)	99 (99.9)
System organ class 1	n (%)	99 (99.9)	99 (99.9)	99 (99.9)
Preferred term 1	n (%)	99 (99.9)	99 (99.9)	99 (99.9)
	n (%)	99 (99.9)	99 (99.9)	99 (99.9)
Preferred term m	n (%)	99 (99.9)	99 (99.9)	99 (99.9)
System organ class	n (%)	99 (99.9)	99 (99.9)	99 (99.9)
Preferred term 1	n (%)	99 (99.9)	99 (99.9)	99 (99.9)
	n (%)	99 (99.9)	99 (99.9)	99 (99.9)
Preferred term m	n (%)	99 (99.9)	99 (99.9)	99 (99.9)
System organ class m	n (%)	99 (99.9)	99 (99.9)	99 (99.9)
Preferred term 1	n (%)	99 (99.9)	99 (99.9)	99 (99.9)
	n (%)	99 (99.9)	99 (99.9)	99 (99.9)
Preferred term m	n (%)	99 (99.9)	99 (99.9)	99 (99.9)

Source: Data listings {Specify data listing number(s)} Analysis dataset: {Specify datasets} Dictionary Name: MedDRA Version: 19.0

Notes: All percentages are based upon the number of enrolled subjects by group.

Subjects with more than one event within a particular SOC and PT will be counted only once for that SOC and PT.

^{*} Patient = Subject with asymptomatic plaque; Control = Healthy volunteer

Version: 01 Page: **103 of 167**

Table 14.3.1.3: Number (%) of Subjects Reporting Treatment Emergent Adverse Events by Severity – Safety Population

PRIMARY SYSTEM ORGAN CLASS PREFERRED TERM	Gra (M	de 1 ild)	Grade 2 (Moderate)		Grade 3 (Severe)		Grade 4 (Threatening/ disabling)		Grade 5 (Death)		Missing		Total	
	Patient*	Control*	Patient*	Control*	Patient*	Control*	Patient*	Control*	Patient*	Control*	Patient*	Control*	Patient*	Control*

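### The treatment-emergent window closes 30 days after injection but the final visit may fall as late as day 33, so AEs with onset on days 31–33 are collected and listed but left out of the AE summary tables

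*SAP*

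**What the plan says.** **TEAE window.** SAP 6.1.3.1 defines treatment-emergent events as those that emerge after the injection and "up to 30 days after the injection that were absent before it or worsen relative to the pre-treatment state". Adverse drug reactions are a subset: "Treatment emergent adverse events possibly or probably related to study treatment".

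**Final visit.** SAP 6.1.12 says that "the visit has to be performed between the 27th and the 33rd day from the" administration of the tracer. The schedules in Protocol Table 1 and SAP 4.3.4 place at this visit an AE assessment and the only scheduled post-dose haematology, coagulation, chemistry, urine and antibody samples. Protocol 10.2 also provides for unscheduled sampling; samples "will be obtained at baseline for screening, 30 +/- 3 days post IP administration and following any adverse events".

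**AE collection.** Protocol 13.1 states: "AEs will be reported, if applicable, from the signing of the informed consent until the last study-related procedure". The same section allows an AE to be any "unfavourable and unintended sign (including an abnormal laboratory finding").

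**AE tables.** The seven AE summary shells, Tables 14.3.1.1 to 14.3.1.7, cover TEAEs, adverse drug reactions and their serious subsets. The overall summary has a row for "Treatment emergent SAEs", and its withdrawal and death rows are restricted in the same way. Protocol 12.5.1 plans to tabulate AEs and SAEs without any such time limit, and SAP section 8 declares no change from the protocol.

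**The concern.** The period over which AEs are collected and the period over which they are summarised do not match. The protocol asks for AEs up to a visit that may validly take place on day 33, while the summary tables accept onsets only to day 30. The gap falls on the one visit at which a late laboratory or immune effect would be looked for.

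Suppose a participant attends on day 32, inside the window, and a new abnormality is recorded as an AE dated to that sample. It is not a TEAE. Because adverse drug reactions are drawn from TEAEs, it cannot be one of those either, even if the investigator judges it related. The same finding in a participant who attended on day 29 would be counted in both. Whether it appears in the AE and reaction rates then depends on which permitted day the participant came in.

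**Working it through.** **Inputs**

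- TEAE upper limit: 30 days after injection (SAP 6.1.3.1).
- Final visit: 30 ± 3 days (Protocol Table 1; SAP 6.1.12).
- Planned participants: 35 patients + 10 controls = 45 (SAP 4.3.5).
- Study day of onset: start date − injection date + 1 for events after the injection date, with the injection day as day 1 (SAP 12.1). The visit schedule calls the injection day Day 0 (Protocol Table 1; SAP 6.1.12).

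**1. The visit window.** 30 − 3 = 27 and 30 + 3 = 33, which reproduces the range in SAP 6.1.12. The permitted days number 33 − 27 + 1 = 7.

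**2. Permitted days after the cut-off.** With the cut-off as start date − injection date ≤ 30, days 31, 32 and 33 lie outside: 3/7 = 42.9%.

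**3. Participants exposed.** The documents give no distribution of visit days, so this rests on an assumption. The figures are for all 45 attending.

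| Assumed share of visits after day 30 | Participants of 45 |
|---|---|
| 0% | 0 |
| 10% | 4.5 |
| 43% (even spread) | 19.3 |
| 60% | 27 |
| 100% | 45 |

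These are participants whose final visit falls after the cut-off. They are not events lost.

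**4. Clinical events.** TEAE status depends on when the event emerges. Taking the 24-hour call as day 1, a visit on day v covers v − 1 possible onset days, of which v − 30 lie after the cut-off.

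| Visit day | Onset days lost | Share of the interval |
|---|---|---|
| 31 | 1 of 30 | 3.3% |
| 32 | 2 of 31 | 6.5% |
| 33 | 3 of 32 | 9.4% |

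**5. Laboratory AEs.** If the abnormality is recorded as an AE and dated to the sample, a sample on days 31–33 puts it wholly outside the window. The documents do not state how such an AE is to be dated.

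**6. Day counting.** If the cut-off were programmed on the SAP 12.1 study-day variable, start date − injection date + 1 ≤ 30 means a difference of at most 29. Days 30, 31, 32 and 33 would then fall outside: 4/7 = 57.1%, including the nominal day-30 visit.

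**7. After the fix.** With the window running to the final visit, 0 of the 7 permitted days fall outside.

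**The case against.** The strongest reply is that very little disappears from the report. Laboratory values and antibody development are safety endpoints in their own right (SAP 6.1.3). SAP 6.1.3.2 calls for descriptive statistics and shift tables, and the 14.3.5 shells compare screening with Visit 3 with no day-30 limit. Clinically significant values go to Table 14.3.4. Deaths and SAEs appear in Tables 14.3.2.1 and 14.3.2.2, which are not restricted to TEAEs, and every AE appears in Listings 16.2.7.1 to 16.2.7.4 with a TEAE flag. The safety analysis is descriptive, and no safety hypothesis rests on these counts. All of this stands, and it is why the point is minor.

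It does not remove the mismatch. The haematology and chemistry shells show means, standard deviations and quartiles, Table 14.3.4 is a listing, and the table index has no immunogenicity table. None of these gives the incidence of AEs or adverse drug reactions, which is what the 14.3.1 tables are for.

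A second reply is that a window tied to the final visit lets follow-up vary from 27 to 33 days. That is true, but the 30-day limit does not equalise follow-up either, because collection for a participant seen on day 27 ends on day 27. It only sets aside events that the protocol required to be collected from those seen later.

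A reader might infer two stronger things that the documents do not support:

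- **That anything found at a day 31–33 visit is lost.** An event that began by day 30 and was first reported on day 32 remains a TEAE.
- **That this visit supplies the only post-dose blood sample.** It is the only scheduled one; SAP 6.1.3.2 has samples at "30 ± 3 days post IP administration and following any adverse events".

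**Conclusion.** The mismatch holds as a matter of text, and its consequence is limited. An AE with onset on, or dated to, days 31–33 is left out of Tables 14.3.1.1 to 14.3.1.7 and cannot be counted as an adverse drug reaction. It remains in the listings, and in Tables 14.3.2.1 and 14.3.2.2 if serious or fatal. Any laboratory values behind it remain in the laboratory outputs.

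Three of seven permitted visit days are affected. The share of participants exposed could be anything from 0% to 100%; about 43% rests on an even spread that the documents neither state nor imply. For clinical events the loss is 1 to 3 onset days. The main exposure is a laboratory abnormality that is new, recorded as an AE and dated to the sample.

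It would be tempting to read 19 of 45 as the number of participants with lost events, or to conclude that AE rates are materially biased downward. Neither follows: the figure counts visit dates under an assumption, and the documents give no rate at which such findings would occur. Severity: minor.

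**What to change.** In SAP 6.1.3.1, define TEAEs as events that start or worsen after the injection, up to and including the date of the participant's final study visit. Use that single cut-off rather than a fixed day number beside it, and let the adverse drug reaction, SAE and serious adverse drug reaction tables follow from it. State that the window is computed from dates with the injection as Day 0, so that the day 1 convention in SAP 12.1 does not shift it.

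The cost is one sentence and one derivation, with no new data. Since Protocol 13.1 ends AE collection at the last procedure, AE counts should stay the same or rise slightly. Protocol 13.2 gives no end date for the onset of reportable SAEs. The sentence should therefore also say how an SAE with onset after an early final visit but by day 30 is classed, so that the change does not drop an event that the present rule would count.
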